#### 5.2 Endpoints

#### 5.2.1 Primary endpoint

#### Patients' autonomy

-CONFIDENTIAL- Page 17 of 33

The rate of self-administered parenteral nutrition at home (autonomy rate), defined as administration without nursing service assistance, as documented within the patient's study diary and calculated as the number of patients with autonomy divided by the total number of patients in the respective arm. Autonomy – as relevant for the primary endpoint – is achieved if the patient self-administers 70% or more of her/his total administrations (Note: Help of family members or other personal caregivers accounts for self-administration).

#### 5.2.2 Secondary endpoints

#### Efficacy endpoints

- Relative weight change determined at baseline and during study visits approx. every four weeks after enrolment;
- Relative change of albumin and CRP levels measured at baseline and during regular study visits;
- Overall survival (OS) defined as the time from randomization to death from any cause.

#### Quality of Life endpoints

- Quality of Life (QoL) through the MODIFIED HPN-PROQ questionnaire;
- To determine the frequency of PN-related visits by the nursing service

#### Safety endpoints

- Catheter related infections (CRI) defined as the presence of bacteraemia originating from the intravenous (port) catheter Bacteraemia must be confirmed through a blood culture according to study site-specific routine, preferably through paired quantitative blood cultures or a culture of the catheter if the catheter is removed OR any infections originating from the intravenous (port) catheter, requiring intravenous antibiotics OR infections in the intravenous (port) catheter, requiring intravenous antibiotics or antibiotics delivered to the catheter itself or catheter removal.

  For the diagnostic procedures to be done to confirm CRI, investigators are recommended to follow the DGHO guidelines.
- Catheter related complications such as line occlusions of catheter-related central venous thrombosis;

-CONFIDENTIAL- Page 18 of 33

- Severe, NCI-CTC common toxicity criteria version 5.0 grade 3-5, infections including fever of unknown origin and other Adverse Events according to NCI-CTC common toxicity criteria version 5.0;
- PN-Related Adverse Events (AEs) and hospitalizations during therapy;

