#### 3.5 Rationale for PEKANNUSS trial

PN at home using traditional 2/3-chambers is associated with a significant limitation and burden to the patients, as they are dependent on home care and nursing for administering the PN and injection of the required nutrition compounds. PN is, therefore, associated with frequent manipulation at the peripheral or central intravenous device. Data indicate that less manipulation on the PN bags before actual application to the patient reduces the hazard of BSI, however, industrially premixed MCB are often unable to entirely meet the patients' needs and

-CONFIDENTIAL- Page 12 of 33

require additional injections of supplements. Multiple line manipulations are required to substitute several nutrition compounds, leading to a high risk of catheter related complications, and limiting subjects' autonomy. Eurotubes® – as ready-to-use system – require less manipulations and are, therefore, expected to be associated with less complications. The Eurotubes® are already used in the clinical routine practice. However, there is no clear recommendation which type of bags should be used in cancer patients, as there are no clinical trials comparing Eurotubes® versus traditional bags with regards to safety, QoL and response to concomitant anti-cancer therapy. Therefore, further research with randomized controlled trials is urgently required.

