#### 4 Study design

This is an open-label, randomized, multicenter, investigator-initiated, phase IV trial. A total number of 216 patients will be enrolled (see chapter 7 for statistical calculations).

Patients with metastatic or localized solid tumors who fulfil the eligibility criteria and who have an indication for parenteral nutrition will be enrolled.

Patients will be stratified according to ECOG (0-1 vs. 2 vs. 3), the modified Glasgow Prognostic Score (mGPS) (0-1 vs. 2) and whether the patient receives concurrent systemic anti-cancer treatment (e.g. chemotherapy, targeted therapy, immunotherapy) or not.

In a first step, patients will be randomized in a 2:1 ratio to Arm A or Arm B:

Arm A: Standard Parenteral Nutrition using Eurotubes®.

or

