**Table 1: Schedule of Assessments** 

Schedule of Assessments	Screening	Visit 1 – Visit 12¹	EOT Visit	Follow- Up 
Informed consent 	X			
ECOG	X 	X	$X^{16}$	
Modified Glasgow Prognostic Score (mGPS)	$X^4$	X	X	
Nutritional Risk Screening	X 			
Physical Examination	X	X	$X^{16}$	
Weight	X	X	$X^{16}$	
Height	X			
Medical History	X			
Demographics, other baseline parameters	X			
Concomitant anti-cancer therapy (if any)	X 	$X^6$	$X^6$	
Laboratory 	X	X	X	
Pregnancy test 	X			
Catheter Related Infections (CRI)	X	X	X	
Any catheter related complications	X	X	X	
Adverse Events 	X	X	X	(X)
Medical device deficiencies 		X	X	
QoL questionnaire 	X	X	$X^{16}$	
Patient's study diary	$X^{12}$	$X^{13}$	$X^{13}$	
HPN therapy plan / administration/documentation		X 	X 	
Post discontinuation PN				$X^{15}$
Overall survival		X	X	X

- (1) A maximum of 12 visits should be documented within the study. The visit schedule itself is up to the clinical routine at the site and may occur approx. every four weeks. However, only the first visit within each four-week interval (starting from randomization) will be documented. If there is more than one visit within a four-week interval, only the first visit will be documented.
- (2) Every 3 months (+/- 2 weeks) until death or end of the study for survival status.
- (3) Mandatory prior to any study procedure.
- Should be (re-)determined by the study personnel even if known through the documentation received by the inpatient facility. Please note: ECOG PS of 0, 1, 2 and 3 are eligible for the trial.
- (5) Any anti-cancer therapy (including surgery and radiation) should be documented.
- (6) Changes in the anti-cancer therapy should be documented
- (7) Routine peripheral blood lab usually done in patients receiving HPN including but not limited to: Complete blood count (German: kleines Blutbild), albumin, total protein level (German: Gesamteiweiß), CRP, GOT (AST), GPT (ALT), LDH, cholinesterase, creatinine, triglycerides, urea, glucose, electrolytes (sodium, potassium, magnesium, calcium, phosphate) should be

-CONFIDENTIAL- Page **30** of **33** 

- determined according to local lab routine. Laboratory assessments do not need to be repeated at screening if laboratory assessments were done prior to screening within clinical routine and results are not older than 2 weeks.

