- (8) In case of women of child-bearing potential. Serum pregnancy test at Screening.
- (9) Adverse Events (related or not) are captured at any time throughout the study as soon as they become known to the study team, beginning after the patient has given written informed consent and up to 14 days after the last study treatment was administered.
- (10) Medical device deficiencies are captured from randomization until last study specific HPN.
- (11) The site staff instructs the patient of how to complete the QoL questionnaire. Questionnaire is completed during all documented study visit until EOT. Results of the completed QoL questionnaire(s) are transcribed to the eCRF by the site.
- The site staff instructs the patient how to complete the patient's study diary. Handing out of a diary covering enough days until the next planned visit. Patient should complete diary daily until EOT. Please note: patients' diary is very important as it includes information on one of the study primary endpoint!
- (13) Results of the completed study diary are transcribed to the eCRF. Handing out of new diaries as needed.
- (14) Adjustments of the PN therapy plan are possible throughout the study, independent from the planned study visits. The latest adjustment will be documented at the time of each visit. The PN is administered at home through the nursing service, a caregiver or the patient.
- (15) After EOT, subsequent HPN/PN will be captured (only manufacturer).
- (16) If results of examinations are available which are not older than 14 days no further examination will be necessary.

**Important note:** These assessments are required by the study protocol. All examinations are part of routine clinical practice. It is important to note that the study protocol does not limit the examinations to the points mentioned above. The investigator shall perform all other/additional routine or site-specific examinations relevant to the safety of the patient or for any other procedures done.

-CONFIDENTIAL- Page 31 of 33

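### Catheter-related infection (CRI) pools culture-confirmed bacteraemia with events that need no culture and are judged by unblinded sites, and the protocol states no analysis that separates them

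*Combined protocol and SAP*

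**What the plan says.** Section 5.2.2 (Safety endpoints) defines CRI by three limbs joined by OR.

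- **Limb 1:** bacteraemia originating from the catheter. "Bacteraemia must be confirmed through a blood culture according to study site-specific routine".
- **Limb 2:** "OR any infections originating from the intravenous (port) catheter, requiring intravenous antibiotics".
- **Limb 3:** infection in the catheter, "requiring intravenous antibiotics or antibiotics delivered to the catheter itself or catheter removal".

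On diagnostic work-up, "investigators are recommended to follow the DGHO guidelines"; this is not mandatory.

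Section 4 states: "This is an open-label, randomized, multicenter, investigator-initiated, phase IV trial". No central or blinded assessment of CRI is described. Section 6.2 allows up to 50 sites. Section 3.5 says that Eurotubes "require less manipulations and are, therefore, expected to be associated with less complications".

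Section 5.1.2 lists CRI as an objective for A versus B and again for A-1 versus A-2. Section 6.3.2 assigns CRI to the per protocol population, compares rates by Fisher's exact test and treats secondary p-values as descriptive. The sensitivity analyses named there change the analysis population and leave the event definition as it is. Further detail is left to a later SAP.

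**The concern.** The three limbs carry different standards of evidence. Limb 1 needs a laboratory result. Limbs 2 and 3 are met once a site attributes an infection to the catheter and treats it in one of the listed ways. The staff making those decisions know the bag in use, and the protocol tells them which bag is expected to do better.

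Detection may also differ without any leaning by investigators. Section 3.2 describes daily nursing visits under usual PN, and section 3.3.3 presents Eurotubes as a way to do without them. It is an inference, not a statement in the protocol, that fewer professional contacts could change how often a local infection is noticed.

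The infection rationale in sections 3.2 and 3.4 concerns bloodstream infection, which limb 1 matches most closely. If only the composite is reported, a reader cannot tell whether a CRI difference comes from confirmed bacteraemia or from the limbs that need no culture.

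**Working it through.** **Does any stated analysis separate the limbs?**

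1. Section 5.1.2 names CRI as a single incidence for both comparisons.
2. Section 6.3.2 gives one test for rates and one population for CRI, and its sensitivity analyses vary only the population.
3. The separate endpoint of grade 3-5 infections in section 5.2.2 is neither culture-based nor catheter-specific, so it does not stand in for limb 1.

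None is stated.

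**How large could the effect be?** The documents give no CRI rate, sample size or power, so there is no plan figure for CRI to reproduce. The only borrowed inputs are the arm sizes in section 6.1: 128 in Arm A and 64 in Arm B, total 192. By the Walters approximation named there, these give 80.5% power for 5% versus 20% autonomy, so the stated size reproduces. The rates below are assumptions.

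*Moderate case.* True CRI is 15% in both arms, split into 7.5% culture-confirmed and 7.5% not confirmed. Arm B records an excess *k* of the unconfirmed part:

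observed rate in B = 7.5% + 7.5% × (1 + *k*)

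- *k* = 0.25: 7.5% + 9.375% = 16.9%; ratio to 15% = 1.13
- *k* = 0.50: 7.5% + 11.25% = 18.75%; ratio to 15% = 1.25

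Exact enumeration of the two-sided Fisher test at 64 versus 128 gives the chance of p ≤ 0.05:

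| Observed B vs A | Chance of p ≤ 0.05 |
|---|---|
| 15% vs 15% (no bias) | 3.7% |
| 16.9% vs 15% | 5.1% |
| 18.75% vs 15% | 8.6% |
| Confirmed only, 7.5% vs 7.5% | 3.3% |

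*Larger cases.* Confirmed CRI is 10% in both arms; unconfirmed CRI is 5% in A and higher in B.

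| Unconfirmed in B | Composite B vs A | Chance of p ≤ 0.05 |
|---|---|---|
| 10% (2-fold) | 20% vs 15% | 12% |
| 15% (3-fold) | 25% vs 15% | 35% |
| 20% (4-fold) | 30% vs 15% | 64% |

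For the confirmed events alone the chance is 3.4% throughout. With confirmed rates of 5% to 15%, the 2-fold row ranges over 11-15% and the 4-fold row over 57-73%.

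In the moderate case the harm is mainly a shifted estimate. A markedly higher chance of a small p-value needs a two- to four-fold excess.

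*Limit of the illustration.* Equal confirmed rates in the two arms are assumed. They would not hold if sites also took cultures more readily in one arm.

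**The case against.** Several counter-arguments have force.

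- **Little depends on it.** CRI is secondary, its p-values are descriptive, and no hierarchy gives it special rank. This stands, and it limits the point to a cheap improvement.
- **Limbs 2 and 3 are anchored.** They do not exclude a culture, they require a recordable treatment, and the guideline recommendation covers the whole definition. This stands in part, because the attribution and the decision to treat are still made by unblinded staff.
- **A partial cross-check exists.** Grade 3-5 infections need no attribution to the catheter and so are less open to this bias. They are also graded by the site and mix in infections unrelated to the catheter.
- **The SAP is still to come, and the eCRF is not shown.** An analysis by limb could be added, and the eCRF may already record the limb. But if the limb is not recorded prospectively, a later SAP may be unable to recover it reliably.

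Two stronger readings should be resisted.

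A reader might take limb 1 as free of bias. The documents do not support that: culturing follows each site's routine, so unblinded staff also decide when to culture. Agreement or disagreement between limb 1 and the composite would not settle whether bias occurred.

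A reader might also infer from Table 1 that a late catheter infection counts as an adverse event but not as a CRI, because CRI is marked only to EOT while adverse events run "up to 14 days after the last study treatment was administered". That does not follow. The CRI definition sets no time limit, Table 1 lists when assessments are made, and the text does not say how long after the last PN the EOT visit falls. Section 9 also has reportable events from other visits entered with the next protocol visit. No change of window is called for.

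**Conclusion.** The point holds as a modest improvement to a secondary safety endpoint. CRI combines one limb that requires a culture with two that do not, unblinded sites make the judgements, and the protocol states no analysis by limb. A composite difference in either comparison could therefore partly reflect attribution or detection. The stated expectation makes a direction plausible for A versus B only, since A-1 and A-2 both use Eurotubes.

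It would go too far to say that the bias occurs or that a CRI result would be invalid; the documents show only that it is possible. The spurious risk ratio of 1.13-1.25 rests wholly on assumed inputs: 15% true CRI, half of it unconfirmed, and a 25-50% excess in Arm B. The primary conclusion on autonomy is unaffected.

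**What to change.** 1. Keep the composite CRI endpoint as defined.
2. Record in the eCRF, for each CRI, which limb or limbs it met, whether a culture was taken, and whether it was positive.
3. Pre-specify in the SAP a table of CRI by limb for A versus B and for A-1 versus A-2, with culture-confirmed CRI (limb 1) as a supportive analysis.
4. State beside that analysis that limb 1 is less susceptible to unblinded judgement but not immune, because culturing is also at the site's discretion.

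The cost is a few eCRF items, if they are not already there, and one extra table. The statistical downside is lower precision. At the assumed 7.5% confirmed rate, about 64 × 0.075 = 4.8 events would be expected in Arm B and 128 × 0.075 = 9.6 in Arm A, half the composite count. The culture-confirmed result should be read as an estimate with its confidence interval, alongside the composite.

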#### 6 Statistical design

The present trial is designed as an open-label, randomized, multicenter, investigator-initiated phase IV trial comparing standard parenteral nutrition using Eurotubes® vs. traditional 2/3-chamber bags in subjects with metastatic or localized solid tumors requiring parenteral nutrition.

The primary endpoint is defined as the frequency of self-administered HPN (patients' autonomy).

#### 6.1 Sample size calculation

For the primary endpoint statistical significance is assessed using a fisher's exact test at a two-sided alpha level of 0.05 for the objective patient autonomy.

The power calculation was carried out using the Power Procedure in SAS version 9.4 (method: Walters normal approximation for unbalanced groups): Considering the 2:1 randomization, 128 patients must be included in Arm A (Standard Parenteral Nutrition using Eurotubes®) and 64 patients in Arm B (Standard Parenteral Nutrition using 2/3-chamber bags), resulting in a sample size of 192 patients, to ensure 80% power to detect an improvement of the objective patient autonomy from 5% with traditional 2/3-chamber bags to 20% with Eurotubes®.

Assuming a dropout rate of about 10% it is planned to include 216patients.

#### **6.2 Study Duration**

Each patient will receive study-specific PN for a maximum of 12 months starting from the date of randomization. Physicians are free to continue PN after the end of this 12 months period if they believe that PN is in the best interest of the patients, but this is done outside the study and is captured in the eCRF as post-discontinuation therapy.

Recruitment is expected to occur over 3 years, followed by a maximum treatment duration of 12 months within the trial and a 6 months period for data cleaning and monitoring resulting in

-CONFIDENTIAL- Page 19 of 33

an expected total study duration of approximately 4.5 years. The study will be conducted at up to 50 sites located in Germany.

#### 6.3 Analysis

Prior to final analysis, data verification with respect to completeness and plausibility (data cleaning) will be performed. Inconsistencies and mistakes will be clarified with the study sites and will be removed. The data cleaning process starts soon after first patients are enrolled and monitored. Major protocol violations and special cases will be listed.

After enrolment of 100 patients an interim analysis will be performed, non-including the primary endpoint.

The study analysis plan (SAP) and the handling of special cases and major violations will be defined and completed prior to study completion and prior to any conduct of analyses.

#### 6.3.1 Study populations for the analysis

The following data sets for analysis are defined:

#### Intent-to-treat population (ITT)

The intent-to-treat (ITT) population includes all patients who were randomized. Treatment assignment is based on the randomized treatment (primary population).

The ITT population is the primary population for the description of the patient and treatment characteristics and is used for the primary efficacy analysis.

#### Per protocol (PP) population

This population will include all randomized patients who fulfill the inclusion and exclusion criteria and received at least two weeks of PN at home according to treatment arm. Treatment assignment is based on the treatment actually given. Sensitivity analyses of the primary endpoint will be performed on the per protocol analysis set.

#### Safety analysis set

The evaluation of safety parameters is carried out in the safety population, which is defined as all randomized patients who received at least one application of PN at home. Treatment assignment is based on the treatment actually given.

-CONFIDENTIAL- Page **20** of **33** 

Several subgroup analyses will be performed including but not limited to NRS score, ECOG classification and whether the patient receives concomitant anti-cancer therapy or not. Further details will be specified in the SAP.

#### 6.3.2 Statistical methods for the analysis

#### Patient Demographics/Other Baseline Characteristics

The following demographic and baseline characteristics will be summarized descriptively by treatment group:

- Gender and age;
- Patients' disease (e.g. colon cancer, breast cancer, gastric cancer);
- Tumor status (localized or metastatic solid tumors);
- Number and type of organs involved in metastatic disease (e.g. liver, lung, lymph nodes, bone);
- Patients history (concomitant disease, number and type of previous anti-cancer therapies);
- Type and start date of the current/concomitant anti-cancer therapy;
- ECOG performance status;
- mGPS
- Nutrition risk screening score;
- Baseline lab values and baseline QoL;
- Other characteristics.
- Type of central catheter used for parenteral nutrition

#### **Primary Endpoint**

The primary analysis will compare patients randomized to Arm A (Standard Parenteral Nutrition using Eurotubes®) with those randomized to Arm B (Standard Parenteral Nutrition using 2/3-chamber bags) regarding the objective patient autonomy and will be based on the ITT population. To test the hypothesis:

H01: "The objective patient autonomy does not differ between the treatment Arms A and B

$$(P_{12} = P_{22})$$
."

VS.

-CONFIDENTIAL- Page 21 of 33

H11: "The objective patient autonomy differs between the treatment Arms A and B  $(P_{12} \neq P_{22})$ ."

fisher's exact test is used with a type I error of 0.05.

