#### Arm B: Standard Parenteral Nutrition using 2/3-chamber bags.

Patients randomized to Arm B will receive PN according to the routine used by the participating site.

Patients in Arm A will be stratified again by the same criteria as listed above and randomized in a 1:1 ratio to Arm A-1 or Arm A-2:

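### Randomisation is stratified by ECOG, mGPS and anti-cancer treatment, but the primary test ignores these factors; a pre-specified stratified CMH test would be a cheap improvement, not the correction of an error

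*Combined protocol and SAP*

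**What the plan says.** Section 4 (Study design) sets the factors for the 2:1 randomisation to Arm A or Arm B: "Patients will be stratified according to ECOG (0-1 vs. 2 vs. 3), the modified Glasgow Prognostic Score (mGPS) (0-1 vs. 2". The third factor is binary and is worded there as "whether the patient receives concurrent systemic anti-cancer treatment". For the 1:1 randomisation to A-1 or A-2 it adds: "Patients in Arm A will be stratified again by the same criteria as listed above".

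Section 6.1 plans the primary comparison as Fisher's "exact test at a two-sided alpha level of 0.05 for the objective patient autonomy". Section 6.3.2 (Primary Endpoint) repeats that Fisher's "exact test is used with a type I error of 0.05" in the ITT population, with no mention of strata and no effect estimate or interval. For secondary endpoints, section 6.3.2 names Fisher's test for rates, the t-test for continuous variables and the log-rank test for OS, again without stratification; those p-values are descriptive.

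The factors otherwise appear in the baseline summaries of section 6.3.2 and, in part, in the subgroup plan at the end of section 6.3.1: "Several subgroup analyses will be performed including but not limited to NRS score, ECOG classification" and concomitant anti-cancer therapy. mGPS is not on that open list. The same place adds: "Further details will be specified in the SAP". No separate SAP is in the text supplied.

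**The concern.** The design balances the arms on three factors and the one confirmatory test then discards them. When the factors predict the outcome, stratified allocation followed by an unstratified test makes the test conservative and forgoes precision that the trial has already paid for in randomisation complexity.

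There is a qualitative reason to expect some prognostic value. Section 3.3.3 ties self-administration of Eurotubes to the patient's general condition, which ECOG measures. Against that, section 5.2.1 notes: "Help of family members or other personal caregivers accounts for self-administration". A frail patient with a helpful relative can therefore still count as autonomous, which may weaken the link. At stake are a few points of power and agreement between design and analysis. The validity of the primary result is not in question.

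**Working it through.** **1. Inputs from the documents.** Arm A 128, Arm B 64, autonomy 20% vs 5%, two-sided alpha 0.05, power 80%, Walters approximation, 216 enrolled after about 10% dropout (section 6.1). Strata: 3 x 2 x 2 = 12 (section 4).

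**2. The plan's own figure.** Walters power = Phi(2 x sqrt(nA nB/(nA+nB)) x [asin sqrt(pA - 1/(2nA)) - asin sqrt(pB + 1/(2nB))] - 1.96).
- pA - 1/256 = 0.1961, arcsine term 0.4587
- pB + 1/128 = 0.0578, arcsine term 0.2428
- multiplier 2 x sqrt(8192/192) = 13.064
- 13.064 x 0.2159 = 2.821, and Phi(2.821 - 1.960) = 80.5%

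At 126/63 the result is 79.8%, so 192 is the smallest 2:1 total that reaches 80%. It reproduces. 192/0.9 gives 214, so 216 is adequate.

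**3. Exact behaviour of the planned Fisher test (full enumeration).**
- Power at 20% vs 5%: 82.6% (128/64) and 88.1% (144/72).
- Power at 144/72 with 10% dropouts counted as failures (0.9 x 20% = 18% vs 0.9 x 5% = 4.5%): 83.1%.
- Size at 144/72 for common rates of 5%, 10%, 15% and 20%: 3.2%, 3.7%, 4.0% and 4.2%.

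The test holds its level conservatively and meets its power target.

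**4. Fisher against a stratified test, by simulation.** There were 40,000 trials per scenario at N=216, with Monte Carlo SE about 0.16 point for power and 0.1 for size. The following are assumptions, not in the documents:
- 2:1 permuted blocks of 6 within strata.
- ECOG / mGPS / treatment mixes of 45-40-15 / 60-40 / 70-30 (mix 1), 70-25-5 / 80-20 / 85-15 (sparse), and even.
- Odds ratios for autonomy: none; moderate (ECOG 2 0.5, ECOG 3 0.2, mGPS 2 0.7, second treatment level 1.5); strong (0.3, 0.08, 0.5, 2.0).

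Marginal rates were held at 20% vs 5%. CMH strata were pooled by the rule given under the fix. Power in %:

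| Mix | Prognosis | Fisher | Chi-square | CMH | CMH, continuity-corrected |
|---|---|---|---|---|---|
| 1 | none | 87.7 | 89.5 | 89.3 | 83.9 |
| 1 | moderate | 87.9 | 89.6 | 90.2 | 84.9 |
| 1 | strong | 88.4 | 90.1 | 91.6 | 86.7 |
| sparse | none | 87.8 | 89.5 | 89.4 | 83.8 |
| sparse | moderate | 88.1 | 89.7 | 89.9 | 84.8 |
| sparse | strong | 88.2 | 89.9 | 90.6 | 85.4 |
| even | none | 87.8 | 89.5 | 89.3 | 83.7 |
| even | moderate | 88.1 | 89.9 | 90.8 | 85.6 |
| even | strong | 88.6 | 90.2 | 92.4 | 87.8 |

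**5. Splitting the gain.**
- CMH minus Fisher: 1.5 to 3.8 points.
- Chi-square minus Fisher, which has nothing to do with strata: 1.6 to 1.8.
- CMH minus chi-square, the effect of stratification itself: -0.2 to +2.2 (none -0.2 to -0.1, moderate +0.3 to +0.9, strong +0.8 to +2.2, before rounding of the table).
- With dropouts as failures: total gain 2.1 to 4.8, of which stratification -0.3 to +2.5.
- At N=192: total gain 2.6 to 5.6, of which stratification -0.5 to +2.6.
- Continuity-corrected CMH has 0.8 to 4.1 points less power than Fisher.
- An exact conditional stratified test differs from Fisher by -0.4 to +2.3 points (10,000 trials each).
- Simulated size: Fisher 2.7-4.2%, CMH 4.6-5.2%.

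**6. Second simulation, N=192, different assumptions** (ECOG 50/35/15%, mGPS 50/50%, treatment 65/35%, 12 unpooled strata). Fisher 82.5-83.0%, chi-square 85.2-85.7%, uncorrected CMH 85.0-87.3%. Stratification itself contributes about -0.4 to +1.7 points. The picture is the same.

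**7. Sparse strata.** In the sparse mix at N=216, the cell with mGPS 2 and the second treatment level expects 216 x 0.20 x 0.15 = 6.5 patients, and 6.5 x 0.70 = 4.5 of them with ECOG 0-1. A pooling rule is therefore sensible. The rule proposed below left every pooled stratum with at least 10 patients in all 63 scenarios run. Against the 12 raw strata it changed CMH size by at most 0.14 point and power by at most 0.5.

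**The case against.** The strongest reply is that nothing is broken. Fisher holds its level, exceeds its power target and is the test for which 192 was derived. With 5% of 64 to 72 patients, about 3 to 4 autonomous patients are expected in Arm B, so an exact test is a defensible choice. About half or more of the gain in most scenarios comes from leaving Fisher's discreteness, which a plain chi-square test also achieves. The upper end of the stratification gain needs strong assumed odds ratios. Keeping Fisher as primary and adding a stratified sensitivity analysis would also answer the consistency point, and the SAP may already provide one.

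Much of this stands. The gain is small, it can be slightly negative when the factors are not prognostic, and the guarantee on size is lost. What does not carry is the appeal to the SAP, because section 6.3.2 already fixes the primary test. Sparse strata are dealt with by the pooling rule, and anyone who wants guaranteed size can use the exact stratified test. Changing the primary test does mean rewording the justification in section 6.1, but not the number: 192 is conservative for uncorrected CMH.

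**Conclusion.** The point holds as a worthwhile, non-blocking improvement. Both randomisations use the three factors and no described between-arm test does. At N=216 the uncorrected CMH test gains 1.5 to 3.8 points of power over Fisher, of which -0.2 to +2.2 is due to stratification. The sizes rest on assumed stratum shares, odds ratios and block size. The factual part and the exact Fisher figures rest only on the protocol. Confidence in a material benefit is moderate, because the protocol has no data linking these factors to autonomy.

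**What to change.** In sections 6.1 and 6.3.2, name as the primary test the CMH test **without** continuity correction, stratified by ECOG, mGPS and concurrent anti-cancer treatment as recorded at randomisation. Keep Fisher as a sensitivity analysis and keep 192/216, stating in 6.1 that the number was derived for Fisher and is conservative for CMH.

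Fix an outcome-blind pooling rule in advance, for example:
1. If either mGPS level has fewer than 10 patients, ignore mGPS.
2. Within each mGPS level, if either treatment level has fewer than 10, ignore treatment there.
3. Within each resulting cell, if ECOG 2 or ECOG 3 has fewer than 10, merge the two; if any remaining ECOG group still has fewer than 10, ignore ECOG in that cell.

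Report the Mantel-Haenszel risk difference with the stratified Miettinen-Nurminen 95% CI using Mantel-Haenszel weights. It excludes 0 exactly when this CMH test rejects. If guaranteed size is preferred, use the exact conditional stratified test instead. Stratifying the OS log-rank test and the A-1 vs A-2 comparisons is optional, for consistency only.

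The cost is protocol and SAP wording and a few lines of code, with no new data or patients. Downsides to state:
- Size is not guaranteed at or below 5% (up to 5.2% simulated, Monte Carlo SE 0.11).
- If the factors do not predict autonomy, stratification loses 0.1 to 0.2 points against chi-square at N=216 (up to 0.3 with dropouts as failures, 0.5 at N=192).
- The simpler Mantel-Haenszel interval with Sato variance covers only 93.3-93.6% at a common 5% rate. The recommended score interval covers 95.2-95.4% there but is conservative at 20% vs 5% (95.3-97.2%).
- The continuity correction must be explicitly switched off.
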